10.3 Data Management

All required data for this clinical study will be recorded via a validated database. This database complies with GCP requirements, laws and regulations applicable to the conduct of clinical trials, ISO 14155, and 21 CFR 11 (US Code of Federal Regulations) pertaining to the use of electronic records and signatures. System training for all research coordinators and Investigators will be conducted through instructor-led training supported with an on-line training module.

Incoming data will be frequently reviewed to identify inconsistent or missing data and any adverse events. Investigators are responsible for the accurate completion and timely submission of the data collected during this trial. Any data issues are to be promptly addressed with the Investigator by the study manager, designated monitor/CRO and/or Sponsor.

Clinical procedures have been established to ensure that complete, accurate and timely data are submitted, that protocol requirements are followed and that adverse events are correctly reported and investigated. Investigators are to maintain all source documents as required by the protocol, including laboratory results, supporting medical records and signed Informed Consent forms. The source documents will be verified during regular monitoring visits to ensure that the clinical data is complete and accurate.

10.4 Adverse Events & Definitions

A complication is defined as any clinical finding that has the potential to become clinically significant in the opinion of the investigator. A complication may progress in the level of clinical significance and become classified as an adverse event. All complications shall be recorded on the CRFs.

Adverse Events (AEs) are clinical findings that result in an untoward medical event.

Please record all AEs on the CRFs. Adverse Events will be further classified as Serious Adverse Events (SAEs) if the event:

- Is life threatening or fatal;
- Results in permanent impairment of a body structure or function;
- Results in congenital anomalies/birth defects
- Requires or prolongs hospitalization; or
- Requires medical or surgical intervention to preclude permanent impairment of a body function or permanent damage to a body structure.

Note: Hospitalization is defined as any initial admission (even if less than 24 hours) to a healthcare facility as a result of a precipitating clinical adverse effect; to include transfer within the hospital to an intensive care unit. Hospitalization or prolongation of hospitalization in the absence of a precipitating, clinical adverse effect (e.g., for a preexisting condition not associated with a new adverse effect or with a worsening of the preexisting condition; admission for a protocol-specified procedure) is not, in itself, a serious adverse effect. The following definitions for rating severity of adverse events will be used:

Mild: Awareness of signs or symptoms, but easily tolerated; are of minor irritant type; causing no loss of time from normal activities; symptoms would not require medication or a medical evaluation; signs or symptoms are transient.

Moderate: Interferes with the subject's usual activity and/or requires symptomatic treatment.

Severe: Symptom(s) causing severe discomfort and significant impact of the subject's usual activity and requires treatment.

AEs or SAEs will also be classified as to their relationship to the device, as follows:

- Not Related:** The event is due to an underlying or concurrent illness or effect of another device, drug or intervention and is not related to the investigational device, procedure or general surgery.
- Possible:** The event has a strong temporal relationship to the use of the investigational device, procedure or general surgery, and an alternative etiology is equally or less likely.
- Probable:** The event has a strong temporal relationship to the use of the investigational device, procedure or general surgery and another etiology is unlikely or significantly less likely.
- Definite:** An event that can only be attributed to the use of the investigational device, procedure or general surgery.
- Not Assessable:** The event’s relationship to the use of the investigational device, procedure or general surgery cannot be assessed.

If an AE or SAE is determined to be probably or definitely related to the investigational device and has not been previously anticipated, the clinical finding would further be classified as an unanticipated adverse device effect (UADE). A UADE is defined as “any serious adverse effect on health or safety or any life-threatening problem or death caused by, or associated with, a device, if that effect, problem, or death was not previously identified in nature, severity, or degree of incidence in the investigational plan or application (including a supplementary plan or application), or any other unanticipated serious problem associated with a device that relates to the rights, safety, or welfare of subjects.”

SAEs that are determined to be probably or definitely related to the investigational device are referred to as device-related serious adverse events (DRSAEs). The protocol definitions for “device failure”, “device malfunction”, and “technical observation” are provided below:

Device Failure: A device has failed if it does not perform according to the Instructions for Use provided with the device and as a result, negatively impacts the treatment, when used according to this protocol. A device failure that causes or contributed to a serious adverse event would be classified as a DRSAE.

Device Malfunction: A device malfunction is an unexpected change to the device that is not contradictory to the labeling and may or may not affect the performance of the device. A device malfunction is not considered to be a DRSAE unless it causes or contributes to a serious adverse event. **Technical Observation:** Malfunction or complaint with a medical device that has the potential to, but may or may not result in, a negative clinical consequence to the patient.

Note: A device failure or device malfunction is considered to be a DRSAE if it causes or contributes to a SAE.

Any Device Failure, Device Malfunction or Technical Observation must also be documented in the CRFs.

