10.5 Reporting of Adverse Events

All adverse events, including SAE’s and UADE’s, will be monitored from the time of enrollment through the

study exit. A description of the event, including the start date, resolution date, action taken, and the outcome shall be provided, along with the Investigator's assessment of the relationship between the AE and the study device and procedure.

All AE's should be followed until the event is resolved or judged to be clinically stable. The clinical site should plan to provide additional, relevant AE follow-up information to the Sponsor upon request.

All SAEs, DRSAEs, and UADE's must be reported to the Sponsor and/or CRO and the primary Investigator at the site **within 24 hours** of the Investigator becoming aware of the event. Additionally, the Investigator should notify their IRB, and local/national authorities as required, within their specified timeframes. The Sponsor and CRO will decide whether all of the local Investigators need to be informed immediately, or whether this can be postponed until the next regularly scheduled study update.

A completed SAE CRF **must** be uploaded to the Sponsor's secure web server **within 7 days of the event**. The minimum required data to be recorded for an SAE includes: date of event, type of event, duration of event, severity, seriousness, action taken, outcome, causality and relationship to the Interscope device and procedure. In the case of a DRSAE, whenever possible, the device involved in the failure or malfunction is to be returned to Interscope for analysis.

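### Section 10.4 says it grades relationship to the device, but every grade pools device, procedure and general surgery, so the device-related SAE label and, through surgery, the safety endpoint can pick up the wrong events

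*Combined protocol and SAP*

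**What the plan says.** Section 10.4 introduces the scale with "AEs or SAEs will also be classified as to their relationship to the device, as follows". The grades that follow do not keep to the device:

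- **Not Related** joins two conditions: "The event is due to an underlying or concurrent illness or effect of another device, drug or intervention", and the event "is not related to the investigational device, procedure or general surgery". Both must hold.
- **Possible** needs a close link in time to the same three-part cause, with a competing explanation that is no more likely.
- **Probable**: "strong temporal relationship to the use of the investigational device, procedure or general surgery and another etiology is unlikely" or clearly less likely.
- **Definite**: "An event that can only be attributed to the use of the investigational device, procedure or general surgery".
- **Not Assessable** refers to the same three-part cause.

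The same section then uses the two upper grades for labels that concern the device alone: "SAEs that are determined to be probably or definitely related to the investigational device are referred to as device-related serious adverse events". The UADE rule uses the same two grades and adds that the event was not anticipated.

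Section 10.5 asks the investigator for an "assessment of the relationship between the AE and the study device and procedure", and lists relationship to device and procedure among the minimum SAE data. It does not say whether that is one rating or two. Section 7.4.2 defines the safety endpoint as absence of SAEs related to the device or to the procedure, and tabulates events on that combined basis.

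**The concern.** The heading of the scale and the wording of its grades ask different questions. An investigator who follows the heading asks whether the EndoRotor caused the event. One who follows the grades asks whether the EndoRotor, the endoscopy or any surgery caused it. With up to ten sites (section 4.5), both readings may be used, and the grades would then not be comparable.

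This matters because the objective in section 4.1 is the safety of this device and the trial has a single arm. No control group shows the background harm of endoscopic necrosectomy, so event-level attribution is the main route to any statement about the device itself. The labels also have uses: under section 10.5 a DRSAE prompts return of a device involved in a failure or malfunction, and under section 9.8 UADEs are reported to FDA.

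**Working it through.** The documents give no figure to reproduce, so the check is of the text.

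**Step 1: count the grades.** Five of the five grades in 10.4 use the pooled cause. No device-only or procedure-only scale appears elsewhere in the protocol.

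**Step 2: apply the written rules to three serious events.** The events are hypothetical.

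| Cause of the event | Grade available in 10.4 | DRSAE if the pooled grade is used | Truly device-related | Counts in 7.4.2 on the pooled grade | Should count in 7.4.2 |
|---|---|---|---|---|---|
| The EndoRotor cutter | Probable or Definite | Yes | Yes | Yes | Yes |
| The endoscope alone | Probable or Definite | Yes | No | Yes | Yes |
| Later surgery for the underlying disease alone | Probable or Definite | Yes | No | Possibly | No |

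The second row mislabels a DRSAE but leaves the endpoint right, because the endpoint accepts procedure-related events. The third row can be wrong on both.

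**Step 3: test whether Not Related rescues the third row.** Later surgery fits the first condition, as another intervention. It fails the second, which requires no relation to general surgery. Both conditions must hold, so on the literal wording the event cannot be graded Not Related.

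**Step 4: is surgery part of the study?** Sections 4.2 and 5.3 describe endoscopic procedures only. Section 5.4 lets the investigator use any medically necessary means during follow-up, so surgery can occur but is not a study intervention.

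**Step 5: UADE.** The definition in 10.4 also requires a serious event not previously identified. Section 6.1 lists bleeding, infection, injury to the GI tract and surrounding tissue, pneumonia, heart attack and stroke. Misgrading can therefore create a UADE only for a serious event outside such lists.

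**Step 6: size for the endpoint.** With 30 treated subjects (section 7.3) and k subjects whose only counted SAE is due to surgery alone, the excess is k/30. The documents give no value for k, so a range is shown:

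- k = 0: 0
- k = 1: 1/30 = 3.3 percentage points
- k = 2: 2/30 = 6.7 percentage points

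A subject who already has an SAE related to the device or procedure adds nothing to k.

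**The case against.** The strongest reply is that section 10.5 already asks about device and procedure for every adverse event, that the CRF is not among the documents and may hold two fields, and that the DRSAE and UADE rules name the investigational device alone, which directs the assessor to it. This stands in part. A reader might infer that the device's own harm cannot be separated, or that the DRSAE and UADE counts are wrong. The documents support neither. They show only that no defined scale or planned table separates the two causes, and that the counts can be wrong. Two CRF fields would not settle the matter either, since the only defined grades are pooled and both fields would carry the same meaning.

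Second, the 7.4.2 endpoint covers device or procedure, so endoscopy events belong in it. This stands fully; only the reference to general surgery can inflate it.

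Third, a reader might take pneumonia after anaesthesia as an event that becomes Definite and then a UADE. It is a listed risk, so it would be anticipated. Many such cases would also have other explanations, and the text leaves open whether sedation belongs to the procedure or counts as another drug or intervention.

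Fourth, a reader might infer that the stopping decision in section 10.2 has no data item behind it. Section 10.5 collects relationship to the procedure, and under 10.2 the DMC and FDA judge relatedness themselves. Nothing ties their decision to the site's grade.

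Finally, over-attribution counts against the device in a descriptive, unpowered study, so the error is in the cautious direction. That is fair and limits the weight of the point. But section 7.1 says the results are to establish a safety profile and inform later studies, and an overstated rate serves neither purpose.

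**Conclusion.** The point holds as a mislabelled scale. Applied as written, it can attach the DRSAE label to events in which the device played no part, and the UADE label to such events if they are serious and unlisted. It also lets an SAE due only to surgery count as related in the 7.4.2 endpoint, at 3.3 percentage points per subject so added.

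The endpoint figure assumes a denominator of 30, no other counted SAE in that subject, and that Probable and Definite count as related; section 7.4.2 does not state which grades do. The DRSAE effect cannot be sized, because the documents give no expected event numbers and no planned table reports the device alone. DMC adjudication under its charter may reduce both effects. This should be corrected, but it does not undermine the trial.

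**What to change.** In section 10.4, replace the single scale with two items that share the same categories:

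- (a) relationship to the EndoRotor device;
- (b) relationship to the study necrosectomy procedure, stating whether sedation is included.

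Delete general surgery from every grade. Treat surgery as another intervention unless it was needed because of (a) or (b). Base DRSAE and UADE on (a), base the 7.4.2 endpoint on (a) or (b), and tabulate the two items separately. In the same edit, say in 7.4.2 which grades count as related, and align its four categories with the five in 10.4 (Not Assessable is absent from 7.4.2).

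The cost is wording in 10.4 with matching lines in 7.4.2, one extra table, and at most one extra CRF field per adverse event if the form does not already have two. No visits or assessments are added.

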10.5 Reporting of Adverse Events

All adverse events, including SAE’s and UADE’s, will be monitored from the time of enrollment through the

study exit. A description of the event, including the start date, resolution date, action taken, and the outcome shall be provided, along with the Investigator's assessment of the relationship between the AE and the study device and procedure.

All AE's should be followed until the event is resolved or judged to be clinically stable. The clinical site should plan to provide additional, relevant AE follow-up information to the Sponsor upon request.

All SAEs, DRSAEs, and UADE's must be reported to the Sponsor and/or CRO and the primary Investigator at the site **within 24 hours** of the Investigator becoming aware of the event. Additionally, the Investigator should notify their IRB, and local/national authorities as required, within their specified timeframes. The Sponsor and CRO will decide whether all of the local Investigators need to be informed immediately, or whether this can be postponed until the next regularly scheduled study update.

A completed SAE CRF **must** be uploaded to the Sponsor's secure web server **within 7 days of the event**. The minimum required data to be recorded for an SAE includes: date of event, type of event, duration of event, severity, seriousness, action taken, outcome, causality and relationship to the Interscope device and procedure. In the case of a DRSAE, whenever possible, the device involved in the failure or malfunction is to be returned to Interscope for analysis.

10.6 Privacy and Confidentiality

Privacy and confidentiality of subjects will be maintained throughout the Interscope ENDOROTOR trial. A unique identification code will be assigned to each patient participating in this trial. Access to the patient's medical records will be limited to authorized personnel of the Sponsor, their designated CRO, clinical site study staff and authorized regulatory authorities as required by the EC and/or local or national agencies. Any data that may be published in abstracts or scientific journals, and/or presented at medical meetings will reference a unique patient code and will not reveal the patient's identity. The Sponsor and their representative (CRO) will make every reasonable effort to protect the confidentiality of the subjects participating in this study.

11.0 STUDY DATA REPORTING AND PROCESSING

11.1 Data Entry, Cleaning and Editing

Development of a validated database for the trial will be performed by Interscope and/or its CRO. Interscope will also be responsible for auditing the database and confirming the overall integrity of the data.

Single data entry into the database will be done by Interscope and/or its CRO. All study records and CRFs will be subjected to initial inspection during routine monitoring visits for omitted data, gross data inconsistencies, and deviations. Any deficiencies or deviations will be resolved by the site. Any discovered errors are referred to the clinical site research coordinator for correction through a Data Clarification Form.

11.2 Final Data Analyses

All exported datasets for analyses by SAS will undergo a final data cleaning procedure using SAS programmed logical routines unique to each exported dataset.

APPENDIX 1 – SCHEDULE OF STUDY ASSESSMENTS

A schedule of study assessments is provided below.

	Baseline	Index Procedure (Day 0)²	Procedures 2 through 4 14 (+7/-0) Days³	Discharge	21 (±7) Days⁴
Confirm Eligibility	X	X			
Informed Consent	X				
Demographics	X				
Medical History	X				
Physical Examination	X				X
SF-36	X				X
Pregnancy Test ¹	X				
EndoRotor® Procedure		X	X		
CT Imaging (Standard of Care)	X				X
Adverse Event Assessment		X	X	X	X

¹ Urine pregnancy test for female of child bearing potential within 1 day of procedure.

² The index procedure must be done within 2 weeks of enrollment with outpatient video documentation of before and final results from procedure.

³ Procedures 2 through 4 at 14 (+7/-0) days is not required if there is at least 70% removal of accessible necrotic debris in the collection being treated.

⁴ Visit based on 21 (+/-7) days from last EndoRotor procedure

APPENDIX 2 - DEFINITIONS

Adverse Device Effect (ADE): An adverse device effect is defined as any untoward adverse event related to the use of an investigational or unintended response to a medical device.

NOTE 1: This definition includes adverse events resulting from insufficient or inadequate Instructions for Use, deployment, installation, operation, or any malfunction of the medical device. This definition includes any event resulting from insufficiencies or inadequacies in the Instructions for Use or the deployment of the device or any event that is a result of user error.

NOTE 2: This definition includes any event resulting from use error or from intentional misuse of the medical device.

Adverse Event (AE): An adverse event (AE) is any untoward medical occurrence, unintended disease or injury, or untoward clinical signs (including abnormal laboratory findings) in subjects, users or other persons, whether or not related to the study device/procedure.

Anemia: Decrease from baseline in red blood cells, hemoglobin, or total blood volume that is associated with hemodynamic changes or requires transfusion, or a drop in hematocrit to below 30%. Any documented anemic event requiring ≥ 2 units PRBCs will be considered an SAE.

Bleeding Complication at Index Procedure: Bleeding requiring intra-procedure intervention is not considered a serious adverse event and while it can occur it can be managed intra procedurally.

Death: (divided into 2 categories)

A. Cardiac death is death due to any of the following:

1. Acute myocardial infarction.
2. Cardiac perforation/pericardial tamponade.
3. Arrhythmia or conduction abnormality.
4. Stroke within 30 days of the procedure or stroke suspected of being related to the procedure.
5. Death due to complication of the procedure, including bleeding, vascular repair, transfusion reaction, or bypass surgery.
6. Any death for which a cardiac cause cannot be excluded.

B. Non-cardiac death is a death not due to cardiac causes (as defined immediately above).

Delayed Bleeding: Bleeding occurring after the patient has been discharged requiring hospitalization and intervention.

Bleeding that occurs post-procedure requiring intervention.

Device Failure: A device that is used in accordance with the Instructions for Use, but does not perform according to the Instructions for Use and negatively impacts the treatment.

Device Malfunction: A malfunction of a device is an unexpected change to the device that is contradictory to the Instructions for Use and may or may not affect device performance. Includes damage, stress fracture or other failure as observed at the procedure.

Endoscopy: An examination or procedure using an endoscope to examine the inside of the alimentary tract.

Infection, systemic: Systemic infection documented by positive lab culture or clinical evidence, requiring medical treatment to treat and resolve.

Perforation: Puncture of the alimentary tract.

Serious Adverse Device Effect (SADE): A serious adverse device effect is defined as an adverse device effect that results in any of the consequences characteristics of a serious adverse event or that might have led to any of these consequences if suitable action had not been taken or intervention had not been made or if circumstances had been less opportune.

Serious Adverse Event (SAE): A serious adverse event (SAE) is defined an adverse event that:

- led to death,
- led to a serious deterioration in the health of the subject, that either resulted in:
- a life-threatening illness or injury, or
- resulted in a permanent impairment of a body structure or a body function, or
- required in-patient hospitalization or prolongation of existing hospitalization, or
- resulted in medical or surgical intervention to prevent life-threatening illness or injury or permanent impairment to body structure or a body function, or,
- led to fetal distress, fetal death or a congenital abnormality or birth defect.

NOTE: Planned hospitalization for a pre-existing condition, or a procedure required by the study plan without serious deterioration in health, is not considered a serious adverse event.

Sepsis: Organ dysfunction, hypoperfusion, or hypotension in the presence of a known or suspected infection.

Unanticipated Adverse Device Effect (UADE): A UADE is an event that occurs that has not been expected to occur with the device or during the course of the study procedures and has not otherwise been identified as a possible risk in the clinical investigations.

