7.4.2 Safety Analysis

All safety data will be displayed and analyzed using descriptive statistical methods. No formal inferential analysis is planned for safety comparisons. The safety endpoint is the absence of any device or procedure related serious significant adverse events (SAEs) within the 21 (+/-7) days following EndoRotor procedure. These will be presented overall and by system organ class and preferred term (PT). This will be conducted on the Safety analysis set overall. Subjects who experience more than one event in a given System Organ Class (SOC) and PT will be counted once within that SOC and PT. The total number of events and the number and percentage of subjects with each event will be reported.

Adverse Events: AEs, SAEs and UADEs will be coded using MedDRA. Treatment Emergent AEs, SAEs and UADEs are defined as events starting or worsening after start of the procedure. The number and percent of patients with Treatment Emergent AEs, SAEs and UADEs will be summarized overall and by primary SOC and preferred term (PT). Subjects who experience more than one event in a given SOC and PT will be counted once within that SOC and PT.

The number and percent of subjects with treatment emergent AEs, UADEs and SAEs will be further presented by severity and by relationship to the device or procedure. In tabulating the severity of AEs on a per subject basis, the greatest severity will be assigned to a subject should there be more than one occurrence of the same AE with different reported severities. Relationship will be categorized as unrelated, possibly, probably and definitely related. The highest level of association will be reported for subjects with different relationships for the same AE.

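### Appendix 2 excludes treated index-procedure bleeding from the SAEs without limit, so a related bleed that meets an SAE criterion can count either as event-free or as an event

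*Combined protocol and SAP*

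**What the plan says.** Under its entry for bleeding complications at the index procedure, Appendix 2 states: "Bleeding requiring intra-procedure intervention is not considered a serious adverse event and while it can occur it can be managed intra procedurally".

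Section 10.4 makes an adverse event serious if, among other criteria, it meets one of these:
- "Is life threatening or fatal"
- "Requires or prolongs hospitalization", where the note on hospitalization extends the term "to include transfer within the hospital to an intensive care unit"
- "Requires medical or surgical intervention to preclude permanent impairment of a body function or permanent damage to a body structure"

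Appendix 2 has its own, similar SAE definition. Neither list exempts bleeding.

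Section 7.4.2 then fixes what is counted: "The safety endpoint is the absence of any device or procedure related serious significant adverse events (SAEs", over the 21 (+/-7) day window.

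Two other Appendix 2 entries touch on bleeding. An anemic event that needs 2 or more units of PRBCs is an SAE. Delayed Bleeding, which includes post-procedure bleeding that requires intervention, carries no exclusion from the SAEs.

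**The concern.** Bleeding is the event this study most needs to count consistently. Section 1.2 calls procedural bleeding the primary risk, section 6.1 puts bleeding that needs intervention among the most common risks, and section 4.3 names only perforation and bleeding as potential complications.

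Appendix 2 removes one class of these bleeds from the SAEs and sets no boundary by severity, length of stay or outcome. Two sites could classify the same bleed differently, each following a written definition. Where the Appendix 2 sentence is applied, the event drops out of the safety endpoint and the event-free rate is biased upward. The 24-hour SAE report is also not triggered. Section 4.7 relies on these data to show the benefit-risk profile.

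**Working it through.** The plan has no figure to reproduce. Section 7.3 says the sample size is not based on statistical considerations, and no target rate is attached to the safety endpoint. The check compares the definitions and then sizes the effect.

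**1. What the sentence covers.** The entry's heading restricts it to the index procedure, and the text requires intervention during that procedure. There is no other condition. The closing words about management describe what can be done and do not limit which bleeds are meant.

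**2. Which of these bleeds meet an SAE criterion.** Stopping a bleed endoscopically does not by itself meet one. The intervention criterion in section 10.4 is tied to preventing permanent impairment or damage. The corresponding item in Appendix 2 can be read as falling under an event that "led to a serious deterioration in the health of the subject, that either resulted in" one of the listed outcomes. A bleed that is life threatening, or that prolongs the stay or leads to intensive care transfer, does meet a criterion in section 10.4.

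**3. What other entries settle.** A bleed with anemia needing 2 or more units of PRBCs has its own SAE rule. Bleeding that occurs after the procedure falls under Delayed Bleeding.

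**4. What remains.** This is a related index-procedure bleed, treated during the procedure, that meets an SAE criterion and is not captured in step 3.

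| Rule followed | SAE? | Endpoint in 7.4.2 | Reporting |
|---|---|---|---|
| Appendix 2, index bleeding entry | No | Event-free | AE form within 7 days (section 8.3, Table 1) |
| Section 10.4 or Appendix 2 SAE definition | Yes | Event | Sponsor told within 24 hours (sections 8.6.1, 10.5) |

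No section gives either row precedence.

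**5. Procedures 2 to 4.** Section 4.2 allows up to 4 EndoRotor procedures. Because the entry is headed for the index procedure, the same bleed at a later procedure has no express exclusion. Classification can therefore depend on the procedure number.

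**6. Size.** Inputs: n = 30 (section 7.3), all assumed to be in the Safety population; x affected subjects; no other events.
- Shift per subject: 1/30 = 3.33 points.
- Event-free rate: (30 − x)/30.
- Exact (Clopper-Pearson) 95% lower limit: 0.025^(1/30) for x = 0, otherwise the 2.5% quantile of Beta(30 − x, x + 1).

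| x | Event-free | Lower limit |
|---|---|---|
| 0 | 30/30 = 100% | 88.4% |
| 1 | 29/30 = 96.7% | 82.8% |
| 2 | 28/30 = 93.3% | 77.9% |

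The limits illustrate precision; the plan does not schedule them. The documents give no rate for such bleeds. As an assumption only, if a proportion p of subjects had one, the chance of at least one in 30 is 1 − (1 − p)^30. That is 26%, 60%, 79% and 96% for p = 1%, 3%, 5% and 10%.

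**The case against.** The best defence is that the sentence means only that needing haemostasis during the procedure does not, by itself, make a bleed serious. On that reading a longer stay or a transfer to intensive care is a separate consequence that section 10.4 still catches. This is plausible and may be what was intended, but the sentence does not say it.

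The safeguards are real:
- The bleed is still recorded as an AE and tabulated by severity and relationship (section 7.4.2).
- The Medical Monitor reviews all adverse events (section 10.1).
- DMC reports list adverse events as well as SAEs, and adjudication under the DMC charter may settle single cases (section 10.2). The charter is not in the documents, so this cannot be judged.
- Related procedural bleeding that is not amenable to endoscopic intervention suspends the study, whatever its SAE label (section 10.2).
- The safety analysis is descriptive, and section 7.1 says the endpoints do not define study success.

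These points limit the consequences. None of them says which definition governs the endpoint count.

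A reader might also infer a contradiction with the serious adverse device effect (SADE) definition in Appendix 2, which includes effects that "might have led to any of these consequences if suitable action had not been taken or intervention had not been made". The documents do not support that inference. This wording lets a SADE be a non-SAE for any kind of event, so a bleed that is one and not the other is what the definition permits.

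**Conclusion.** The point holds in a narrow form and should be fixed. For a related index-procedure bleed that is treated during the procedure, meets an SAE criterion and is not captured by the anemia or Delayed Bleeding entries, the documents give two answers and no order of precedence. Each such subject moves the event-free rate by 3.3 points, assuming 30 subjects in the Safety population. How many there would be cannot be estimated from the documents.

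Three stronger readings are not supported. The first is that every treated bleed is misclassified: step 2 shows that ordinary controlled bleeds need not conflict. The second is that the affected bleeds escape independent review: adverse events appear in DMC reports, and the suspension rule works without the SAE label. The third is that this sentence makes the primary endpoint of section 4.3 wrong. That endpoint refers to major complications without defining them, which is a separate problem and adds no weight here.

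**What to change.** Replace the Appendix 2 sentence with: *Bleeding requiring intervention during any EndoRotor procedure is recorded as an AE and is an SAE if it meets any SAE criterion of section 10.4 or Appendix 2.* This also removes the distinction between the index and later procedures.

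Reconcile section 10.4 with the bleeding entry and the SAE definition in Appendix 2, so that one SAE definition decides the safety endpoint in section 7.4.2.

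The cost is wording only, with no new data collection. The reported event rate may be slightly higher, and bleeds that become SAEs will need 24-hour reporting and DMC review.
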